4.3 Safety Analysis Set

The safety analysis set (SAF) consists of all subjects who receive any amount of study drug, and thus is equivalent to the FAS. The SAF will be used for summaries of the safety data as well as study drug exposure, prior and concomitant medications, and posttreatment medications.

4.4 Pharmacokinetics Analysis Set

The pharmacokinetics analysis set (PKAS) is a subset of the FAS. It consists of subjects who receive study drug and for whom at least 1 blood sample is collected and assayed for measurement of enfortumab vedotin and MMAE serum/plasma concentrations and for whom the time of sampling and the time of dosing on the day of sampling is known.

The PKAS is used for all tables and graphical summaries of the pharmacokinetic data.

5 SUMMARY OF ENDPOINTS

5.1 Primary Efficacy Endpoint

The primary efficacy endpoint for this study is confirmed ORR per RECIST Version 1.1 by investigator assessment.

Confirmed ORR is defined as the proportion of subjects whose best overall response (BOR) is a confirmed CR or confirmed PR according to RECIST Version 1.1 as assessed by investigator. Definition of BOR is specified in Section 5.2.5.1. The primary analysis population for confirmed ORR is RES.

5.2 Secondary Efficacy Endpoints

The secondary efficacy endpoints include duration of response (DOR) per RECIST Version 1.1 by investigator assessment, disease control rate (DCR) per RECIST Version 1.1 by investigator assessment, PFS per RECIST Version 1.1 by investigator assessment, OS and safety endpoints.

5.2.1 Duration of Response Per Investigator Assessment

DOR is defined as the time from the date of first documented response (CR or PR that is subsequently confirmed) as assessed by investigator to the date of first documented radiological disease progression (PD) per RECIST Version 1.1 or death due to any cause, whichever occurs first. DOR will only be calculated for subjects who achieved a confirmed CR or PR. DOR will be censored as the following:

- If a subject has neither PD nor death, DOR will be censored at the date of last evaluable radiological tumor assessment.
- If a subject starts a new anti-cancer treatment before any PD event or death, DOR will be censored at the date of last evaluable radiological tumor assessment prior to the date of new anti-cancer treatment.
- If a subject has PD or death immediately after two or more consecutive missed radiological tumor assessments, DOR will be censored at the last evaluable radiological tumor assessment prior to two or more missed radiological tumor assessments.
- If a subject does not have subsequent evaluable postbaseline radiological assessment, DOR will be censored at the first CR/PR date.

For a subject who is censored, the last evaluable radiological tumor assessment refers to the subject's last radiological tumor assessment where the response is CR, PR or SD.

New anti-cancer treatment includes therapies captured on new anti-cancer therapy eCRF and new radiation/palliative radiation therapies captured on new radiation therapy eCRF that will impact target and/or non-target lesions.

DOR (in months) will be calculated as:

$$[(\text{Date of documented progression or death or censoring}) - (\text{Date of the first CR/PR that is subsequently confirmed}) + 1] / 30.4375$$

When a cutoff date is applied to DOR analysis, tumor assessment, death and new anti-cancer treatment occurring after the cutoff date will be excluded from the analysis.

The primary analysis population for DOR is RES who achieved a confirmed CR or PR.

5.2.2 Disease Control Rate per Investigator Assessment

DCR is defined as the proportion of subjects with BOR of confirmed CR or confirmed PR or stable disease (SD), per RECIST Version 1.1 as assessed by investigator. Definition of BOR is specified in Section 5.2.5.1. The primary analysis population for DCR is RES.

5.2.3 Progression-free Survival per Investigator Assessment

PFS is defined as the time from the date of first dose of study drug to the date of first documented radiological disease progression (PD) per RECIST Version 1.1 by investigator assessment or death due to any cause, whichever comes first. PFS will be censored as the following:

- If a subject has neither PD nor death, PFS will be censored at the date of last evaluable radiological tumor assessment.
- If a subject starts a new anti-cancer treatment before any PD event or death, PFS will be censored at the date of last evaluable radiological tumor assessment prior to the date of new anti-cancer treatment.
- If a subject has PD or death immediately after two or more consecutive missed radiological tumor assessments, DOR will be censored at the last evaluable radiological tumor assessment prior to two or more missed radiological tumor assessments.
- If a subject does not have evaluable postbaseline radiological assessment, PFS will be censored at the first dose date of study drug.

For a subject who is censored, the last evaluable radiological tumor assessment refers to the subject's last radiological tumor assessment where the response is CR, PR or SD.

New anti-cancer treatment includes therapies captured on new anti-cancer therapy eCRF and new radiation/palliative radiation therapies captured on new radiation therapy eCRF that will impact target and/or non-target lesions.

PFS (in months) will be calculated as:

$$[(\text{Date of documented disease progression or death or censoring}) - (\text{Date of first dose of study drug}) + 1] / 30.4375$$

When a cutoff date is applied to PFS analysis, tumor assessment, death and new anti-cancer treatment occurring after the cutoff date will be excluded from the analysis.

The primary analysis population for PFS is FAS.

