5.3 Exploratory Endpoints

5.3.1 Time to Response per Investigator Assessment

Time to response (TTR) per RECIST Version 1.1 by investigator assessment will be calculated as the time from the first dose of study drug to the first documented objective response (CR or PR that is subsequently confirmed) per investigator assessment. TTR will only be calculated for subjects who achieved a confirmed CR or PR per investigator assessment. The primary analysis population for DCR is RES who achieved a confirmed CR or PR.

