6.4.2.3 PFS per Investigator Assessment

PFS per RECIST Version 1.1 by investigator assessment will be summarized for each cohort in the FAS. Number and percentage of subjects with an event and each event type (death, PD), censoring and each censoring type (no event, start new anti-cancer treatment before PD or death) will be summarized. PFS will be analyzed using Kaplan-Meier methodology and Kaplan-Meier plots will be provided. The median, first quartile, third quartile and the corresponding two-sided 95% CIs will be calculated. The PFS rate at months 6, 12, 24 and 36 will be summarized along with the corresponding 95% CI if applicable.

6.4.2.4 OS

OS will be summarized for each cohort in the FAS. Number of subjects with event and censoring will be summarized. OS will be analyzed using Kaplan-Meier methodology and Kaplan-Meier plots will be provided. The median, first quartile, third quartile and the corresponding two-sided 95% CIs will be calculated. The OS rate at months 6, 12, 24, 36 will be summarized along with the corresponding 95% CI if applicable.

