7 REVISION AND RATIONALE

Version	Date	Changes	Comment/rationale for change
1.0	05-Feb-2020	NA	Document finalized
2.0	11-Feb-2022	Section 2.2 Study design was updated that subjects enrolled into Cohort 6 are reallocated to Cohort 7 and Cohort 8 based on tumor histology	Per protocol amendment 2, the mixed histology gastroesophageal cancer cohort (Cohort 6) will be split into Cohort 7 and Cohort 8 based on tumor histology to help refine efficacy signal and understand the strength of signal in each histology type.
		Section 2.2 and 5.3.2 Central images will be read after minimum number of responders at stage 1 are met based on BOP2 design	Per updates in protocol amendment 2
		Section 5.2 Update definition for DOR and PFS to censor subject who has PD or death immediately after ≥ 2 missed tumor assessment	Update definition for DOR and PFS per FDA feedback
		Section 5.4 Update SAE definition to include important medical event process Change AESI of ocular disorders to dry eye, and corneal disorders and blurred vision	
 Due to transition of always serious term process to important medical event process To reflect the latest search criteria for AESI
		Section 5.3.5 and 6.4.3.4 Update postbaseline ATA definition Clarify that postbaseline ATA will be summarized by baseline ATA status	
 Add granularity to positive ATA definition Add clarification of ATA summary
		Section 6.2.4 Add additional types of prior systemic therapy Update summary for relapse status based on different cohort	
 To provide details on prior systemic therapy of interest Align with eligibility criteria in protocol amendment 2
		Section 6.4 Remove efficacy analysis for "overall" Remove sensitivity analysis for DCR for subjects who have been followed up for at least 6 months Remove exploratory analysis for biomarker	
 Efficacy analysis is more meaningful for each distinct cancer type Primary analysis for each cohort will ensure all subjects in the cohort have been followed for at least 6

Version	Date	Changes	Comment/rationale for change

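### The missed-scan bullet in the PFS censoring list of SAP 5.2.3 names DOR instead of PFS; the intent is recoverable, but the word and the tabulated censoring types need correcting

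*SAP*

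**What the plan says.** SAP 5.2.3 defines PFS from first dose to first radiological PD or "death due to any cause, whichever comes first". It opens its list of rules with "PFS will be censored as the following". Three of the four bullets name PFS. The third reads "If a subject has PD or death immediately after two or more consecutive missed radiological tumor assessments, DOR will be censored" at the last evaluable scan before the missed ones.

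SAP 5.2.1, under its own opening "DOR will be censored as the following", holds the same missed-scan bullet word for word, and there it belongs.

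The version 2.0 entry in SAP 7 records the change as "Update definition for DOR and PFS to censor subject who has PD or death immediately after ≥ 2 missed tumor assessment" and attributes it to FDA feedback. I use the log only as evidence of what was meant.

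For reporting, SAP 6.4.2.3 says that "censoring and each censoring type (no event, start new anti-cancer treatment before PD or death) will be summarized". SAP 6.4.2.1 gives the same two types for DOR.

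SAP 5.3.1, which defines TTR, closes with "The primary analysis population for DCR is RES who achieved a confirmed CR or PR".

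**The concern.** The bullet decides whether a subject is an event or censored, and at what time. Read literally, it repeats a DOR rule already given in 5.2.1 and sets nothing for PFS. No other current section gives RECIST PFS a missed-scan rule: Protocol 9.4.2.3 has no censoring rules, and the row for missed assessments in Table 1 of SAP 5.3.3.4 serves only the iRECIST endpoints of cohort 9.

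A programmer who followed the word would let the general PFS definition apply and count PD or death after the gap at its late date. Three things would follow:

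- PFS per BICR, which SAP 5.3.2 derives in the same way as PFS per investigator, would be affected too.
- In cohort 9, RECIST PFS and iPFS would treat scan gaps differently, so part of any difference between them could come from this wording.
- The PFS rates at 6, 12, 24 and 36 months in SAP 6.4.2.3 could credit progression-free time during which nobody looked.

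**Working it through.** The plan states no figure on this point, so there is none to reproduce. The check compares the two readings.

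**Inputs.** The formula in SAP 5.2.3 is PFS in months = (date of event or censoring − date of first dose + 1) / 30.4375. Scan intervals are 56 days for cohorts 1 to 8 and 84 days after 1 year on treatment (SAP 2.2). For cohort 9 the first scan is at 63 days, then every 42 days (Protocol 4.1).

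**Single subjects.** Each has one evaluable scan, then two missed scans, then PD at the next. Days are counted from first dose. The week-52 start in the second row is nominal; the shift does not depend on it.

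| Schedule | Last scan | Missed | PD | Literal: event at | Intended: censored at | Difference |
|---|---|---|---|---|---|---|
| Cohorts 1–8, 8-weekly | week 16 (day 112) | weeks 24, 32 | week 40 (day 280) | 281/30.4375 = 9.23 | 113/30.4375 = 3.71 | 168/30.4375 = 5.52 |
| Cohorts 1–8, 12-weekly | week 52 (day 364) | weeks 64, 76 | week 88 (day 616) | 617/30.4375 = 20.27 | 365/30.4375 = 11.99 | 252/30.4375 = 8.28 |
| Cohort 9, 6-weekly | week 9 (day 63) | weeks 15, 21 | week 27 (day 189) | 190/30.4375 = 6.24 | 64/30.4375 = 2.10 | 126/30.4375 = 4.14 |

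Each subject also changes from censored to event. On the literal reading, the first one counts as progression-free at month 6 with no scan between weeks 16 and 40. On the intended reading, that subject leaves the risk set at 3.71 months.

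**A confirmed responder.** Take PR at week 8, confirmed four weeks later and still PR at week 16, then the same gap and PD at week 40. DOR is censored under 5.2.1 at (112 − 56 + 1)/30.4375 = 57/30.4375 = 1.87 months. Literal PFS has an event at 9.23 months.

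**Median PFS.** This is an illustration on assumed inputs: 40 subjects, exponential PFS with a true median of 4 months, 8-week scans, and a given share of subjects with two missed scans just before PD is found. Mean Kaplan-Meier median over 1,000 runs, in months:

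| Share affected | Literal | Intended |
|---|---|---|
| 0% | 4.89 | 4.89 |
| 5% | 5.13 | 5.15 |
| 10% | 5.41 | 5.43 |
| 20% | 5.85 | 5.88 |

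The two readings differ by at most 5.88 − 5.85 = 0.03 months.

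**Censoring types.** The lists in 5.2.1 and 5.2.3 each contain four situations: no PD or death, new therapy first, PD or death after missed scans, and no evaluable postbaseline scan. Sections 6.4.2.1 and 6.4.2.3 name only the first two. A subject censored because PD or death followed a gap did have an event and need not have started new therapy, so neither type fits. The fourth situation has its own rule but no type of its own.

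**The case against.** The strongest reply is that only one reading makes sense. The opening of the list governs all four bullets, a DOR rule there would be redundant, and DOR does not exist for most of the FAS on which PFS is analysed. That stands. A reader might infer that PFS has no missed-scan rule at all, but the documents do not support this: the rule is there under the wrong endpoint name.

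A reader might also take the two-item list in 6.4.2.3 as proof that the rule is absent for PFS. It is not, because 6.4.2.1 omits the same type for DOR, where the rule is explicit. What the lists do show is a reporting gap, which exists on the intended reading and for both endpoints.

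The code cannot be seen and may already follow the intent. The version 4.0 log says that the two-missed-visits derivation for iPFS is kept in the ADaM specifications; whether RECIST PFS is treated there too is not stated. This too stands, and it is why the fix includes a check. Unequal handling of DOR and PFS can arise only in confirmed responders, since a subject with SD has no DOR.

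Finally, the sentence in 5.3.1 could be read as a DCR analysis among responders, where DCR would be 100% by construction. The plan specifies no such analysis: SAP 4.2, 5.2.2 and 6.4.2.2 put DCR on the RES, and 6.4.3.1 states the TTR population correctly. It is a separate wording slip and adds no weight to the PFS point.

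**Conclusion.** Wrong as written, and minor. One operative bullet names the wrong endpoint, and its intent can be recovered from its own list and from the revision log. If the bullet were programmed literally, each affected subject would change status, and the time would move by 4.1 months (cohort 9), 5.5 months (cohorts 1 to 8) or 8.3 months (cohorts 1 to 8 after 1 year) in the cases worked.

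How often this would happen is unknown. The effect on median PFS is probably small, but that rests on the simulation's assumed inputs, which did not examine the landmark rates. PFS is a secondary endpoint summarised by Kaplan-Meier without a test. Confirmed ORR, the BOP2 boundaries, iPFS and iDOR do not depend on the bullet. The gap in the tabulated censoring types is real for DOR and PFS alike.

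**What to change.** 1. In the third bullet of SAP 5.2.3, replace DOR with PFS, and check that the ADaM specification and the code for PFS, per investigator and per BICR, censor at the last evaluable scan before the gap.
2. In SAP 6.4.2.1 and 6.4.2.3, add two censoring types: PD or death following two or more consecutive missed assessments, and no evaluable postbaseline assessment.
3. In the last sentence of SAP 5.3.1, replace DCR with TTR, so that it agrees with 5.2.2, 6.4.2.2 and 6.4.3.1.

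The cost is two one-word replacements, two added categories in each of two sections, and one check of the programming. No new data are needed. If the code already follows the intent, the derivation does not change and only the censoring tables gain rows.

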9.4.2.3 Progression-free Survival

PFS is defined as the time from start of study treatment to first documentation of PD per RECIST Version 1.1 or death due to any cause, whichever comes first. PFS will be analyzed using Kaplan-Meier methodology and Kaplan-Meier plots will be provided. The median PFS and its 2-sided 95% CI will be calculated.

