For cohorts 1 to 8, Imaging scan and disease assessment will be performed at screening/baseline and repeated every 8 weeks (56 days \pm 7 days) from the first dose of study treatment throughout the study until the subject has radiologically-confirmed disease progression, initiates a new subsequent anticancer therapy, dies, withdraws consent, is lost to follow-up or the study closes, whichever occurs first. After 1 year on study treatment, the frequency of disease assessment will be reduced to every 12 weeks (84 days \pm 7 days). Subjects who discontinue study treatment for reasons other than radiologically-confirmed disease progression by RECIST Version 1.1 will enter into a post treatment follow-up period and continue to receive imaging scans every 8 weeks (56 days \pm 7 days) until the subject has radiologically-confirmed disease progression, initiates a new anticancer therapy, dies, withdraws consent, is lost to follow-up or the study closes, whichever occurs first.

In cohort 9, the first on-study imaging will be performed 9 weeks (63 days \pm 7 days) from the first dose of study treatment and then every 6 weeks (36 days \pm 7 days) throughout the study until the subject has radiologically-confirmed disease progression (iCPD per iRECIST), initiates a new subsequent anticancer therapy, dies, withdraws consent, is lost to follow-up or the study closes, whichever occurs first. After 18 months on study treatment, the frequency of disease assessment will be reduced to every 9 weeks (\pm 7 days). Subjects with unconfirmed progressive disease per iRECIST guidelines (iUPD) [Seymour et al, 2017] who are clinically stable may continue on study treatment until progression is confirmed by the investigator (confirmed progressive disease [iCPD]) at the next imaging assessment 6 weeks (\pm 7 days) after iUPD. Treatment with pembrolizumab will be discontinued once the subject has received a maximum of 35 administrations of pembrolizumab (approximately 2 years).

Subjects in cohort 9 who discontinue study treatment for reasons other than radiologically confirmed disease progression per iRECIST will enter into a post treatment follow-up period and have physical exams, ECOG and disease assessments every 6 weeks (\pm 7 days) up to 18 months after first dose, then every 9 weeks (\pm 7 days) until the subject has radiologically

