5.3.3.1 Best Overall Response per iRECIST (iBOR)

iBOR is determined based on all available timepoint tumor response data for a participant. Participants will be classified by best response on study in order of iCR, iPR, iSD, iUPD, iCPD, and NE as outlined in iRECIST criteria. For best overall response of iSD, iSD must be documented as present at least 7 weeks after first dose. For confirmed iCR or iPR, response must be confirmed at a subsequent timepoint that is at least 4 weeks from the first documentation of iCR or iPR. Confirmatory scan for iUPD must occur at least 4 weeks after the date that iUPD was first observed but no longer than 8 weeks.

5.3.3.2 iORR

iORR with confirmed response is defined as the proportion of participants whose iBOR is a confirmed iCR or confirmed iPR per iRECIST as assessed by investigator. Definition of iBOR is specified in Section 5.3.3.1.

5.3.3.3 iDCR

iDCR with confirmed response is defined as the proportion of participants whose iBOR is a confirmed iCR or confirmed iPR or iSD per iRECIST as assessed by investigator. Definition of iBOR is specified in Section 5.3.3.1.

5.3.3.4 iPFS

iPFS is defined as the time from the start of study treatment to the first iUPD which is subsequently confirmed per iRECIST (iCPD) as assessed by investigator or death due to any cause whichever comes first.

Table 1 iPFS Definition

Situation	Date of Event or Censor	Outcome
No evaluable post-baseline imaging assessments, no death	Date of first dose (Day 1)	Censor
Death before first documented iUPD and subsequent anticancer therapy and not after two or more consecutive missed assessments	Date of death	Event
Documented iCPD (confirmed progression) before subsequent anticancer therapy and not after two or more consecutive missed assessments	Date of the initial iUPD that is subsequently confirmed	Event
Documented iUPD and the subject is not clinically stable to continue on treatment	Date of iUPD	Event
Documented iUPD without subsequent scans before subsequent anticancer therapy and the subject is no longer in response follow-up	Date of iUPD	Event
Documented iUPD and all subsequent assessments are iUPD(s) or NE(s) and the subject is no longer in response follow-up	Date of iUPD	Event
None of the above and subsequent anticancer therapy started	Date of last disease assessment prior to start of subsequent anticancer therapy	Censor

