6.9.2 Imputation Rules for Incomplete Dates

Every effort will be made to resolve incomplete death dates. If a partial date cannot be resolved, and subject's death status is Yes, the following imputation methods will be used to complete the missing information:

- If year and/or month is missing, death date will not be imputed. Subject will be censored at the last known alive date.
- If year and month are present but date is missing, death date will be imputed as the midpoint of the earliest and the latest feasible date when last known alive date and analysis cutoff date are taken into consideration, as the examples shown in the table below.

Incomplete Date of Death (YYYY MMM DD)	Last Known Alive Date (YYYY MMM DD)	Analysis Cutoff Date (YYYY MMM DD)	Imputed Date of Death (YYYY MMM DD)
2018 APR ??	2018 MAR 15	2018 MAY 01	2018 APR 15
2018 APR ??	2018 MAR 15	2018 APR 15	2018 APR 08
2018 APR ??	2018 APR 10	2018 MAY 01	2018 APR 20
2018 APR ??	2018 APR 10	2018 APR 20	2018 APR 15

In case of partial starting date of new anti-cancer therapy and new radiation therapy, the date will be imputed to the first day of the month but no earlier than the last dosing date of the study drug. A month and year must be present or the date will remain missing.

Partial or missing date of prior therapy: for start date, the date will be imputed to the first day of the month; for the end date, the date will be imputed to the last day of the month but no later than 14 days before the first dose of the study drug. A month and year must be present or the date will remain missing.

Missing or partial start and stop dates of AEs and concomitant medication will be imputed using the following algorithm:

- Imputation rules for partial or missing stop dates:

- If the month and year are present, then impute as the last day of that month.
- If only the year is present, impute as December 31 of that year.
- If the stop date is entirely missing, assume the event or medication is ongoing.
- Imputation rules for partial or missing start dates:

Start Date		Stop Date						missing
		Complete: yyyymmdd		Partial: yyyymm		Partial: yyyy		
		< 1 st dose	≥ 1 st dose	< 1 st dose yyyymm	≥ 1 st dose yyyymm	< 1 st dose yyyy	≥ 1 st dose yyyy	
Partial: yyyymm	= 1 st dose yyyymm	2	1	2	1	n/a	1	1
	≠ 1 st dose yyyymm		2		2	2	2	2
Partial: yyyy	= 1 st dose yyyy	3	1	3	1	n/a	1	1
	≠ 1 st dose yyyy		3		3	3	3	3

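### Read literally, SAP 5.2.3 censors at first dose subjects who die before any evaluable scan, against the SAP's own PFS definition

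*SAP*

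**What the plan says.** **Event definition.** SAP 5.2.3 counts radiological PD "by investigator assessment or death due to any cause, whichever comes first". Protocol 9.4.2.3 agrees: time from start of treatment "to first documentation of PD per RECIST Version 1.1 or death due to any cause, whichever comes first". The protocol gives no censoring rules for PFS.

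**Censoring bullets in SAP 5.2.3.**
1. "If a subject has neither PD nor death, PFS will be censored at the date of last evaluable radiological tumor assessment".
2. New anticancer treatment before any PD or death: censor at the last evaluable scan before that treatment.
3. PD or death straight after two or more missed scans: censor at the last evaluable scan before the gap. This bullet names DOR although it stands in the PFS section.
4. "If a subject does not have evaluable postbaseline radiological assessment, PFS will be censored at the first dose date of study drug".

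For a censored subject, the last evaluable scan is one read as CR, PR or SD. PFS is analysed in the FAS, that is, all treated subjects.

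**Cohort 9, iPFS (SAP 5.3.3.4, Table 1).** The row for censoring at day 1 reads "No evaluable post-baseline imaging assessments, no death". The next row makes an early death an event at its date: "Death before first documented iUPD and subsequent anticancer therapy and not after two or more consecutive missed assessments".

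**Reporting.** SAP 6.4.2.3 asks for PFS rates at months 6, 12, 24 and 36, and names two censoring types: no event, and new treatment before PD or death. SAP 5.3.2 and 6.4.3.2 derive and analyse PFS per BICR in the same way as PFS per investigator.

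**The concern.** The fourth bullet covers every treated subject without an evaluable scan after baseline and does not ask whether the subject has died. Someone who dies in week 5 meets the event definition and the fourth bullet at once, and nothing in SAP 5.2.3 says which prevails. If the bullet prevails, the shortest PFS times leave the risk set on day 1 instead of counting as failures. That censoring depends on the outcome and can only raise the Kaplan-Meier curve. Each cohort is single-arm, so no control group carries the same bias. In cohort 9, one early death would be an event for iPFS and a censored observation for PFS.

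**Working it through.** The plan states no PFS sample size, event count or power, so there is no PFS figure to reproduce. The check is first textual, then a sizing under stated assumptions.

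**Step 1: does another bullet rescue an early death?** Take a subject who dies in week 5 with no scan after baseline.
- Bullet 1 does not apply, because it requires no death.
- Bullet 2 does not apply without new treatment.
- Bullet 3 does not apply. The first scan is due at week 8 or 9, so none has been missed, let alone two.
- Bullet 4 applies as worded: censored at first dose.
- iPFS Table 1 gives the opposite result for the same subject: event at date of death.

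Two further gaps appear. Because evaluable is described as CR, PR or SD, a subject whose only scan shows PD could also be caught by bullet 4 on a strict reading. And a subject with no evaluable scan who dies after two missed assessments is sent by bullet 3 to a scan that does not exist.

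**Step 2: size.** Let a share q die before any evaluable scan, and let S(t) be true PFS at a time t after the first scan. With n subjects and no other censoring before t, n·S(t) are event-free at t. Counting the deaths, Kaplan-Meier gives n·S(t)/n = S(t). With those subjects censored on day 1, it gives n·S(t)/[n(1−q)] = S(t)/(1−q).

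With n = 40 and an illustrative true rate of 30% (12 subjects event-free):

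| q (assumed) | Early deaths | 1/(1−q) | 30% becomes |
|---|---|---|---|
| 2.5% | 1 | 1.026 | 12/39 = 30.8% |
| 5% | 2 | 1.053 | 12/38 = 31.6% |
| 10% | 4 | 1.111 | 12/36 = 33.3% |
| 15% | 6 | 1.176 | 12/34 = 35.3% |
| 20% | 8 | 1.250 | 12/32 = 37.5% |

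**Step 3: a rough anchor for q.** The documents give no early-death rate for these cohorts. Assume a constant hazard, so q = 1 − 2^(−t/m), with t the time to first scan and m the median OS:
- Week 8, t = 56/30.4375 = 1.84 months. With m = 12.88 (enfortumab vedotin arm of the phase 3 urothelial study, Protocol 2.2.1.3), q = 9.4%. With m = 8.97 (its chemotherapy arm), q = 13.3%.
- Week 9, t = 63/30.4375 = 2.07 months. With m = 12.3 (pembrolizumab alone in first-line HNSCC with CPS ≥ 1, Protocol 2.5.1), q = 11.0%.

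These are probably upper values. Entry requires ECOG 0 or 1, cohort 9 excludes a life expectancy under 3 months, and some early deaths will follow an unscheduled scan. The first two also come from another tumour type.

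**Step 4: check of the factor.** In 3000 simulated cohorts of 40 with 8-weekly scans (exponential times, median OS 12.88 and median PFS 5.6 months), there were on average 3.82 deaths before the first scan. The 6-month rate was 49.1% with those deaths as events and 54.2% under bullet 4, before rounding a ratio of 1.106. The formula gives 1/(1 − 3.82/40) = 1.106.

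**Step 5: two smaller inconsistencies.** In iPFS Table 1, a death after an iUPD that reverted to iSD or iPR, with no iCPD, matches no event row and falls to a censoring row. Separately, SAP 2.2 gives the cohort 9 interval as "then every 6 weeks (36 days", while six weeks are 6 × 7 = 42 days, as in Protocol 4.1 and 7.1.1.

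**The case against.** The strongest reply is that bullet 4 was never meant for subjects with an event. Death is in the definition; bullet 3 names death where the SAP means to censor one; iPFS Table 1 handles the case properly; and neither censoring type in SAP 6.4.2.3 fits an early death. On this view bullet 4 only supplies a date for an event-free subject for whom bullet 1 has no scan to use. That is a plausible account of intent, and it stands to this extent: a reader who concludes that early deaths certainly will be dropped goes beyond the text. It does not settle the matter. Bullets 1 and 2 state their condition and bullet 4 does not, and bullet 3 shows that the list may override a death. The list in SAP 6.4.2.3 also omits the missed-assessment censoring of bullet 3, so it is not exhaustive.

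The second reply is that little hangs on it. PFS is secondary and summarised by Kaplan-Meier, with no test, threshold or planned historical comparison. Subjects with measurable disease who die early stay in the RES as non-responders (SAP 4.2 and 6.9.2) and are OS events (SAP 5.2.4). All of this stands. So does the point about precision: for a 30% rate in 40 subjects the standard error is √(0.30 × 0.70/40) = 7.2 points, against a shift of 3.3 points at q = 10%. The shift is nevertheless systematic and in one direction.

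**Conclusion.** The wording is wrong as it stands. SAP 5.2.3 contradicts its own PFS definition, the protocol's definition and the SAP's iPFS table. If programmed literally, it biases PFS upward in every cohort with a death before an evaluable scan, and PFS per BICR with it. Later rates rise by about 1/(1−q), 1.05 at 5% and 1.11 at 10%, where q is assumed and there is no other censoring before the time point. Confirmed ORR, the BOP2 decisions and OS are not affected by this bullet.

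Three stronger readings are tempting, and the documents do not support them.
- **That median PFS must lengthen by a set amount.** PD is recorded only at scans, so the median can stay put. With q = 10% and an assumed 38% progressing at each 8-weekly scan, PFS is 0.90 × 0.62 = 0.558 after scan 1 and 0.90 × 0.62² = 0.346 after scan 2; under bullet 4 it is 0.62 and 0.384. Both curves cross 50% at scan 2.
- **That the 36-day figure causes wrong censoring.** The documents give no window for a missed assessment. The SAP's revision table places that derivation in the ADaM specifications, so no effect can be shown.
- **That OS loses deaths by the same route.** SAP 6.9.2 has its own rule for deaths with an unknown month. It applies only after efforts to resolve the date, is likely to be rare, and is a separate matter.

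**What to change.** Replace the fourth bullet of SAP 5.2.3 with wording to this effect:

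> A subject with no evaluable scan after baseline, no PD and no death is censored on the date of first dose. A death or PD with no earlier evaluable scan after baseline is an event on its own date, unless it comes after two or more consecutive missed assessments; in that case PFS is censored on the date of first dose.

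This brings PFS into line with iPFS Table 1 for early deaths, protects a subject whose only scan shows PD, and gives a date for a death after two missed scans with no evaluable scan before them. In the third bullet, correct DOR to PFS.

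Two minor edits can go in with it. In iPFS Table 1, make a death after a reverted iUPD with no iCPD an event, under the same conditions on new therapy and missed assessments as the other rows. In SAP 2.2, bring the cohort 9 day count into line with the protocol's 42 days.

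The cost is SAP wording and the matching derivation. No data collection or sample size changes. Reported PFS may be somewhat lower than under the literal rule.
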